5.3 Lifestyle Considerations

The patients must be willing to comply to the following restrictions during the entire study duration, i.e., from screening to the End of Study/Early Termination visit.

5.3.1 General Restrictions

- Contraception requirements: Women of childbearing potential and male patients with a partner of childbearing potential are expected to use adequate methods of contraception during dosing of study medication and for at least seven (7) days after the last dose of study medication (see Exclusion Criteria 1 and 3, Section 5.2).

- Activity: Study patients must refrain from strenuous exercise (defined as greater than 70% of the maximal pulse rate for 1 hour or more) for 72 hours before each blood collection for clinical laboratory tests (except screening).
- Blood donation: The patients must not donate blood or plasma during the study participation
- Participation in other clinical studies: Study patients are not allowed to participate in any other clinical study during the study period.

5.3.2 Prior and Concomitant Medication and Therapy/Procedures

The patients are not allowed to concomitantly use any medication or therapy during the study likely to influence the outcome of this clinical trial. This includes:

- Agents affecting digestive organs
 - PPIs (e.g., omeprazole, pantoprazole, lansoprazole (except study medication), rabeprazole, esomeprazole, dexlansoprazole, dexrabeprazole, vonoprazan, etc.),
 - H₂ receptor antagonists (e.g., cimetidine, ranitidine, famotidine, nizatidine, niperotidine, roxatidine, lafutidine, ebrotidine, etc.),
 - muscarinic receptor 3 antagonists (e.g., atropine, scopolamine, hyoscyamin, ipratropium, tiotropium, pirenzepine, darifenacin, oxybutinin, refefenacin, etc.),
 - gastrointestinal prokinetic agents (e.g., metoclopramide, cisapride, domperidone, bromopride, alizapride, clebopride, itopride, cinitapride, mosapride, etc.),
 - anti-cholinergic agents (e.g., pirenzepine, telenzepine),
 - prostaglandins (e.g., misoprostol, enprostil, etc.),
 - antacids,
 - anti-gastrin agents (e.g., proglumide, oxethazaine, etc.).
- Medications that may affect the metabolism of X842 or linaprazan (cytochrome P450 [CYP] inhibitors and inducers) and medications that may be affected by X842 or linaprazan (substrates of CYP enzymes and drug transporters). For a comprehensive list, see Section 10.9 (Appendix 9),
- Medications contraindicated for use in combination with lansoprazole,
- Medications with reported drug–drug interactions with lansoprazole (warfarin, clopidogrel, ketoconazole, itraconazole, digoxin, tacrolimus, theophylline, methotrexate) and
- *H. pylori* eradication therapy (antibiotics along with PPI).

Patients are not permitted to undergo surgical intervention (e.g., fundoplication) for reflux disease or other antireflux procedures during study participation. Any planned major surgery within the duration of the study is exclusionary.

5.4 Screen Failures

Screening failures are defined as patients who consent to participate in the clinical study but are not subsequently randomized/entered into the study. A minimal set of screening failure information is required to ensure transparent reporting of screening failure patients to meet the Consolidated Standards of Reporting Trials (CONSORT) publishing requirements and to respond to queries from regulatory authorities. Minimal information includes demography, screening failure details, eligibility criteria and any SAE.

Patients who do not meet the criteria for participation in this study may be rescreened once. If the re-screening occurs less than 3 months after the first screening visit, serology tests do not need to be repeated.

6 Study Drug

Study drug is defined as any investigational intervention(s), marketed product(s), or placebo intended to be administered to a study patient according to the study protocol.

6.1 Study Drugs Administered

Study Drug Name:	X842	X842 Dummy	Lansoprazole	Lansoprazole Dummy
Dosage Formulation:	Immediate release tablet	Tablet	Capsule	Capsule
Unit Dose Strength(s)/Dosage Level(s):	X842 25 or 50 mg	Placebo for X842	Lansoprazole 30 mg	Placebo for lansoprazole
Route of Administration:	Oral	Oral	Oral	Oral
Dosing Instructions:	
4-week double-blind treatment
 
X842 25 mg BID 2 tablets (X842 25mg + X842 dummy) and 1 capsule (lansoprazole dummy) in the morning, and 2 tablets (X842 25 mg + X842 dummy) in the evening.
 
X842 50 mg BID 2 tablets (X842 50 mg + X842 dummy) and 1 capsule (lansoprazole dummy) in the morning, and 2 tablets (X842 50 mg + X842 dummy) in the evening.
 
X842 75 mg BID 2 tablets (X842 50 mg + X842 25 mg) and 1 capsule (lansoprazole dummy) in the morning, and 2 tablets (X842 50 mg + X842 25 mg) in the evening.
 
X842 100 mg BID 2 tablets (X842 50 mg×2) and 1 capsule (lansoprazole dummy) in the morning, and 2 tablets (X842 50 mg×2) in the evening.
 
Lansoprazole 30 mg QD 2 tablets (X842 dummy×2) and 1 capsule (lansoprazole 30 mg) in the morning, and 2 tablets (X842 dummy×2) in the evening.
 
4-week lansoprazole 30 mg QD
 
For all patients continuing on open-label phase: lansoprazole 30 mg 1 capsule in the morning.
			
Packaging and Labeling:	Study drug will be provided in blister pack. Each blister pack will be labeled as required per country requirement.	Study drug will be provided in blister pack. Each blister pack will be labeled as required per country requirement.	Study drug will be provided in blister pack. Each blister pack will be labeled as required per country requirement.	Study drug will be provided in blister pack. Each blister pack will be labeled as required per country requirement.

6.2 Preparation/Handling/Storage/Accountability

The blister packs containing the study medication will be dispensed as per randomization schedule by a site pharmacist or a registered nurse under supervision of other site personnel.

The Investigator will maintain a Drug Dispensing Log detailing the dates and quantities of study medication received, dispensed to and used by each patient and study medication returned or destroyed at the end of the study. Any discrepancies between dispensed and returned study drug must be explained and documented. Products deliberately and/or accidentally destroyed by the Investigator/pharmacy or the patient, must be accounted for. Patients will receive one additional blister pack at Visit 2/Day 0 to keep overage in case they return within the allowed visit window. Patients should return this additional blister pack for accountability at every visit and returned on Visit 5.

6.3 Measures to Minimize Bias: Randomization and Blinding

6.3.1 Randomization

Patients will be randomized to receive either one of the four doses of the test product (48 patients per dose group) or the reference product lansoprazole (48 patients).

The randomization list will be generated, and the original randomization list will be kept.

All patients will be centrally randomized using an Interactive Voice Response System (IVRS). Each patient will be assigned a unique number (randomization number) that encodes the patient's assignment to one of the five arms of the study, according to the randomization schedule generated by Parexel using a validated computer program. Details of the procedure are described in the IVRS Manual provided to all clinic/investigational sites.

Randomization will be set as approximately 50% of patients with LA grade A or B and approximately 50% of patients with LA grade C or D.

6.3.2 Blinding

This is a double-blind study and the allocation of treatments will not be disclosed until the file has been declared clean and the database has been locked.

The IMP tablets will be identical in appearance (dummy, 25 mg and 50 mg tablets) and lansoprazole, the reference treatment (capsule), will be identical in appearance as its dummy. All efforts will be made at the clinic/investigational site to maintain the blind. All study medication will be provided in blister packs according to the randomization list through IVRS.

6.3.3 Emergency Unblinding During the Study

The treatment code may only be broken by the Investigator in case of emergency when knowledge of the treatment received is necessary for the proper medical management of the patient.

In case of emergency the Investigator may contact the Sponsor's Medical Monitor for drug specific input prior to disclosure of the treatment allocation. However, the Investigator will make the decision to unblind the treatment assignment.

For unblinding procedures in case of a potential suspected unexpected serious adverse reaction (SUSAR), refer to Section 8.4.6.1.

6.4 Study Drug Compliance

The first administration will take place as early as possible after randomization until 2 pm on Day 0, or at 8 pm on Day 0. Diary cards will be handed out together with the study drug to the patients and they will be instructed to document date and time of the following administrations on the diary card. The patients will bring the diary card at each visit to the study clinic/investigational site. In addition, the patients will also bring the remaining capsules and tablets for reconciliation. Treatment compliance will be based on the number of remaining capsules and tablets.

6.5 Return and Destruction of Investigational Medicinal Products

Any unused study medication will be returned to the Sponsor and/or CRO for destruction. Used/unused blisters will be destroyed at the study sites after reconciliation by the Clinical Research Associate (CRA). The CRA will perform final study drug accountability reconciliation at the study end to verify that all unused study drug is adequately destroyed/returned and documented.

6.6 Prior and Concomitant Therapy

The patients are not allowed to concomitantly use any medication or therapy likely to influence the outcome of this clinical trial. This includes: agents affecting digestive organs (PPIs, H₂ receptor antagonists, muscarinic receptor 3 antagonists, gastrointestinal prokinetic agents, anti-cholinergic agents, prostaglandins, antacids, anti-gastrin agents), medications involved in the metabolism of X842 and linaprazan (CYP substrates, inhibitors, inducers and transporter inhibitors, as specified in Appendix 9), medications contraindicated for use in combination with

lansoprazole, medications with reported drug–drug interactions with lansoprazole (warfarin and clopidogrel) and *H. pylori* eradication therapy.

For list of medication or therapy that are not allowed concomitantly, see Section 5.3.2. Other concomitant medications that the patient receives on a regular basis may continue, if in the opinion of the Investigator, it does not put the patient at undue risk or does not interfere with the study evaluations.

Any change in concomitant medication during the course of the study will be recorded by the Investigator in the relevant section of the case report form (CRF).

6.6.1 Rescue Medication

All restrictions regarding the use of medications or therapies which are likely to influence study outcome are applicable for the entire duration of the study (please refer to Section 5.3.2 for not permitted medications).

6.7 Dose Modification

Dose modification for an individual patient is not allowed.

6.8 Intervention After the End of the Study

There will be no treatment with X842 or lansoprazole available, provided by Sponsor, after End of Study participation. Following discontinuation of study treatment some patients may need additional therapy for their erosive esophagitis due to GERD. The Investigator should ensure patients re-establish care with a physician during the open-label treatment period in order to avoid a lapse.

7 Discontinuation of Study Drug and Patient Discontinuation

7.1 General Withdrawal Criteria

Patients are free to discontinue their participation in the study at any time and for whatever reason without affecting their right to an appropriate follow-up investigation or their future care. If possible, the reason for withdrawal of consent should be documented.

Patients may be discontinued from the study at any time at the discretion of the Investigator for any of the following reasons:

- Severe non-compliance to study protocol procedures, as judged by the Investigator and/or Sponsor

- Significant AEs posing a risk for the patient, as judged by the Investigator and/or Sponsor
- Withdrawal of informed consent by the patient. If consent is withdrawn, the patient will not receive any further study treatment or further study observation. Note that the patient may need to undergo additional tests to withdraw safely
- Withdrawal of informed consent by the patient to the use of biological samples as judged by the Investigator and/or Sponsor
- At the discretion of the Investigator, when he/she believes continued participation is not in the best interest of the patient
- Positive pregnancy test (Pregnant women should be followed until delivery as described in Section 8.4.8)
- Severe laboratory abnormalities (please refer to Treatment and follow-up of AEs in Section 8.4.7):
 - Alanine aminotransferase (ALT) or aspartate aminotransferase (AST) $> 8 \times$ upper limit of normal (ULN)
 - AST or ALT $> 5 \times$ ULN (for more than 2 weeks)
 - ALT or AST $> 3 \times$ ULN with total bilirubin (TBL) $> 2 \times$ ULN (unless elevated bilirubin is related to confirmed Gilbert's Syndrome) or with international normalized ratio (INR) > 1.5
 - ALT or AST $> 3 \times$ ULN with the appearance of fatigue, nausea, vomiting, right upper quadrant pain or tenderness, fever, rash, and/or eosinophilia ($> 5\%$)
- Diagnosis of a malignancy during study (excluding carcinoma in situ of the cervix, or squamous or basal cell carcinoma of the skin).
- The Sponsor or a Regulatory Agency requests withdrawal of the patient.

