8.4.1.3 Adverse events of special interest (AESI)

An AESI (serious or non-serious) is one of scientific and medical concern specific to the Sponsor's product or program, for which ongoing monitoring and rapid communication by the Investigator to the Sponsor can be appropriate. Such an event might warrant further investigation in order to characterize and understand it.

All AESI, serious and non-serious, **must be reported within 24 hours** of identification using the same reporting process as for SAE reporting.

The following conditions should be considered AEs of special interest and require expedited reporting:

- a. ALT or AST $\geq 8 \times$ ULN
- b. ALT or AST $\geq 5 \times$ ULN for 2 or more weeks
- c. ALT or AST $\geq 3 \times$ ULN **and** total bilirubin $\geq 2 \times$ ULN (or ALT or AST $\geq 3 \times$ ULN **and** INR > 1.5)
- d. ALT or AST $\geq 3 \times$ ULN accompanied by clinical symptoms believed to be related to hepatitis or hypersensitivity, such as new or worsening of fatigue, nausea, vomiting, right upper quadrant pain or tenderness, fever, or rash
- e. ALT or AST $\geq 5 \times$ ULN but $< 8 \times$ ULN and cannot be monitored at least weekly for ≥ 2 weeks

Hy's Law, defined as $\geq 3 \times$ ULN ALT or AST **with coexisting** $\geq 2 \times$ ULN total bilirubin with no alternative explanation for the biochemical abnormality other than IMP (for example elevated ALP indicating cholestasis, viral hepatitis, other medication) must always be reported without delay as an AESI, and, if applicable, also as an SAE.

All potential drug-induced liver injuries (PDILI) events require immediate action, testing, and monitoring. If tests are done locally for more rapid results, a concurrent sample should also be sent to the central laboratory whenever possible.

PDILI events require notification of the Medical Monitor within 24 hours (e.g., by laboratory alert), and the patient must be discussed with the Medical Monitor as soon as possible. Patients with PDILI must be assessed to determine if the study drug must be discontinued (please refer to General withdrawal criteria, Section 7.1).

To ensure patient safety and enhance reliability in determining the hepatotoxic potential of an investigational drug, a standardized process for identification, monitoring and evaluation of liver events has to be followed.

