Every liver laboratory trigger or liver event as defined in Table 2 should be followed up by the Investigator or designated personnel at the trial site as summarized below (please also refer to General withdrawal criteria, Section 7.1).

A. Liver laboratory trigger:

- Repeating the LFT within the next week to confirm elevation. The repeat assessment can be done as an unscheduled study visit or at a local laboratory. In this case, local laboratory normal ranges should be recorded, and the results should be made available to the trial investigator immediately, and the data recorded on the CRF.
- If the elevation is confirmed, close observation of the patient will be initiated, including consideration of treatment interruption if deemed appropriate.

B. Liver event:

- Repeating the LFT as soon as possible to confirm elevation as appropriate
- Monitoring of liver chemistry values at least twice per week until values normalize, stabilize, or return to within baseline value
- Discontinuation of the investigational drug if appropriate
- Hospitalization of the patient if appropriate
- A causality assessment of the liver event via exclusion of alternative causes (e.g., disease, co-medications)
- An investigation of the liver event which needs to be followed until resolution.

These investigations can include serology tests, imaging and pathology assessments, hepatologist's consultancy, based on investigator's discretion. All follow-up information, and the procedures performed should be recorded on appropriate CRF pages, including the liver event overview CRF pages.

Table 2 Liver Event and Laboratory Trigger Definitions

	Definition/ threshold
A. LIVER LABORATORY TRIGGERS	ALT or AST > 3 × ULN, but ALT and AST ≤ 5 × ULN TBL > 1.5 × ULN, but TBL ≤ 2 × ULN
B. LIVER EVENTS	
Laboratory events (any of the listed criteria)	ALT or AST > 5 × ULN ALP > 5 × ULN TBL > 2 × ULN (in the absence of known Gilbert syndrome) Potential Hy's Law cases (defined as ALT or AST > 3 × ULN and TBL > 2 × ULN [mainly conjugated fraction] without notable increase in ALP to > 2 × ULN)
Adverse events (any of the listed criteria)	Any clinical event of jaundice (or equivalent term) ALT or AST > 3 × ULN accompanied by (general) malaise, fatigue, abdominal pain, nausea, or vomiting, or rash with eosinophilia Any adverse event potentially indicative of a liver toxicity *

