8.4.8 Pregnancy

In case of pregnancy or suspicion of possible pregnancy, the study treatment must be stopped immediately, and the patient discontinued from participation in the study. Pregnancy itself is not regarded as an AE unless there is a suspicion that the IMP may have interfered with the effectiveness of the contraceptive medication. However, the outcome of all pregnancies (spontaneous miscarriage, elective termination, normal birth or congenital abnormality) must be followed up and documented even after the patient was discontinued from the study.

All events of congenital abnormalities/birth defects are SAEs. Pregnancy complications or spontaneous miscarriages should also be reported and handled as AEs or SAEs. All outcomes of pregnancy must be reported to the Sponsor or Designee by the Principal Investigator on the pregnancy outcomes report form. Follow-up must be performed until delivery or pregnancy termination.

The Investigator will attempt to collect pregnancy information on any female partner of a male study patient who becomes pregnant while participating in this study, and report to Sponsor or Designee. The partner will also be followed to determine the outcome of the pregnancy.

Any pregnancy that occurs during study participation must be reported to the Sponsor or Designee on the pregnancy form, immediately or within 24 hours of the Investigator learning of its occurrence.

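### No available text makes stopping study drug mandatory for an individual patient who meets a liver threshold in Protocol 7.1

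*Protocol*

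**What the plan says.** Protocol 7.1 opens its list of withdrawal reasons with "Patients may be discontinued from the study at any time at the discretion of the Investigator for any of the following reasons". Four liver thresholds sit in that list:

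- ALT or AST above 8 × ULN
- ALT or AST above 5 × ULN for over 2 weeks
- ALT or AST above 3 × ULN with total bilirubin above 2 × ULN (unless explained by Gilbert's syndrome) or INR above 1.5
- ALT or AST above 3 × ULN with listed symptoms or eosinophilia

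The list also contains withdrawal of consent, with the added sentence "If consent is withdrawn, the patient will not receive any further study treatment or further study observation", a positive pregnancy test, and the item "The Sponsor or a Regulatory Agency requests withdrawal of the patient". For pregnancy, Protocol 8.4.8 says that "the study treatment must be stopped immediately, and the patient discontinued from participation in the study".

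On potential drug-induced liver injury (PDILI), Protocol 8.4.1.3 says "Patients with PDILI must be assessed to determine if the study drug must be discontinued (please refer to General withdrawal criteria, Section 7.1". For a Table 2 liver event (path B), the step on stopping drug reads "Discontinuation of the investigational drug if appropriate". The steps listed ahead of it are a prompt recheck of the raised value and then liver tests two or more times a week until they settle. For a Table 2 laboratory trigger (path A) the test is repeated within a week. If the rise is confirmed, the patient is closely observed and interruption is to be considered.

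**The concern.** A withdrawal criterion set at Hy's Law biochemistry or at 8 × ULN normally works as an instruction. Here the operative words leave it to the investigator. One who carries out every required step could keep such a patient on blinded drug, and two sites could handle the same laboratory result differently.

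The liver is the organ of interest in this programme. Every adverse event of special interest (AESI) in 8.4.1.3 is hepatic. Protocol 2.3.1 reports raised liver tests in a small number of patients on linaprazan, the active metabolite. It attributes them to high peak concentration and argues that X842 lowers that peak by about 75%. This reduces the expected risk but does not settle what happens to a patient who crosses a threshold. The stopping rules in 10.1.9 act on the whole study, and 9.6 provides no data monitoring committee.

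**Working it through.** The plan has no figure of its own to reproduce. The check is of the text, followed by simple day counts.

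**1. Does any visible sentence require a stop?**

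- Protocol 7.1 is permissive in its lead-in. The liver item refers to 8.4.7.
- Protocol 8.4.7 leaves treatment of adverse events to the investigator and sends AESIs to 8.4.1.3.
- Protocol 8.4.1.3, on PDILI, makes the assessment mandatory and refers back to 7.1 for the stop. The references form a loop that ends at the permissive lead-in.
- Path B makes stopping conditional ("Discontinuation of the investigational drug if appropriate").
- Path A only asks for interruption to be considered. It matters because some 7.1 cases may reach no further than path A. ALT between 3 and 5 × ULN with INR above 1.5, normal bilirubin and no symptoms meets a 7.1 threshold but need not meet any Table 2 liver-event criterion.
- Protocol 10.1.9 allows a hold after one related SAE. It ends the study at three Hy's Law cases on X842, or at five AESIs of one type at twice or more the comparator's frequency. None of these is a rule for the individual patient.
- SAP 4.4.2 names withdrawal-criteria deviations as a category but sets no stop rule.

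No mandatory individual stop at a liver threshold was found.

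**2. How much blinded dosing could follow?** Table 1 puts safety laboratories at screening, Day 7 (±2), Day 28 (−2/+5) and Day 56. Blinded dosing ends at the Day 28 visit.

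Threshold met at the Day 7 visit, days left = end visit − laboratory visit:
- planned: 28 − 7 = 21
- shortest: 26 − 9 = 17
- longest: 33 − 5 = 28

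Above 5 × ULN for more than 2 weeks, taken as at least 15 days after a first value at the Day 7 visit:
- planned: 28 − (7 + 15) = 6
- shortest: 26 − (9 + 15) = 2
- longest: 33 − (5 + 15) = 13

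This threshold is therefore met on Day 22 as planned, and on Day 20 at the earliest within the visit windows. A threshold first found at Visit 5 leaves no blinded dosing. Laboratory turnaround, which the documents do not give, shortens every figure.

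**3. What would a mandatory stop cost in efficacy data?** SAP 4.10.1.3 counts a missing healing result as not healed. One patient stopped without a Week 4 endoscopy lowers the arm's rate by at most:
- 1/48 = 2.1 points, with 48 randomized per arm
- 1/40 = 2.5 points, with 200 evaluable / 5 arms = 40

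The loss arises only if that patient would otherwise have been recorded as healed. It is larger if the FAS erosive set leaves fewer than 40 in the arm.

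**The case against.** The best counter-argument is that 7.1 was meant to bind. Section 8.4.1.3 asks whether drug must be stopped and names 7.1 as the place to look, and it repeats that pointer before the action lists. SAP 4.4.2 treats breaches of withdrawal criteria as deviations, which makes little sense if the criteria are optional. The item "The Sponsor or a Regulatory Agency requests withdrawal of the patient" sits under the same lead-in and is hardly for the investigator to decide, so the lead-in looks generic. All of this stands as evidence of intent. It makes the text ambiguous but does not supply the missing rule.

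Two stronger readings are tempting, and the documents do not support them:

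- A reader might infer that liver stops were deliberately left optional, because consent withdrawal and pregnancy have their own stop wording and the liver thresholds have none. The Sponsor or regulator item has no such wording either, so its absence shows nothing about intent.
- A reader might take "Discontinuation of the investigational drug if appropriate" as the rule for 7.1 thresholds. It covers every Table 2 liver event, and several fall short of 7.1: a single ALT above 5 × ULN, isolated ALP above 5 × ULN, isolated bilirubin above 2 × ULN. Conditional wording is right for those.

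It is also fair to say that liver events are closely managed. The Medical Monitor is told within 24 hours and the case is discussed, path B requires laboratory checks at least twice weekly and a causality work-up, and the Sponsor can ask for withdrawal. These safeguards narrow the gap to the stop decision itself.

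Finally, a rule could sit in material not available here: the Safety Management Plan, the Medical Monitoring Plan (both cited in Protocol 10.2.3), or Protocol Appendices 5 and 6, which the contents page lists but the copy reviewed lacks.

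**Conclusion.** The point holds as a gap in wording that is worth correcting. On the text available, stopping at a 7.1 liver threshold is discretionary as written, although 8.4.1.3 suggests that a binding stop was intended. Confidence is medium because of the unavailable material.

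The exposure at stake is at most about 21 planned blinded days (17 to 28), or about 6 (2 to 13) for the two-week threshold. These ceilings assume that the investigator continues dosing after Medical Monitor discussion and PDILI assessment, and that neither the Sponsor nor a regulator requests withdrawal. A reader might infer that patients were in fact kept on drug for such periods, or that liver safety went unmanaged. The documents show neither. They give no incidence, so no expected number of cases can be stated.

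The SAP amendment is dated April 2023 and was written after unblinding, so corrected wording can no longer protect patients in this trial's blinded phase. Its practical use is in the Phase 3 protocol that this study supports.

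**What to change.** 1. In 7.1, put the four liver thresholds, and pregnancy in line with 8.4.8, under a statement that study drug must be stopped. Leave the judgement-based reasons under investigator discretion.
2. For thresholds that rest on a single value, hold dosing at once, repeat the liver tests (and INR where it defines the threshold) promptly, and stop permanently if confirmed. For above 5 × ULN lasting more than 2 weeks, which repeat values have already confirmed, stop at once.
3. Use the same hold-then-stop wording in 8.4.1.3 for both path A and path B whenever a 7.1 threshold is met. Keep the conditional wording for liver events below 7.1.
4. Optionally, say in 6.7 that this hold is not a prohibited dose modification. Path A already contemplates interruption, so this only removes doubt.

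The cost is a short amendment, missed doses when a value is not confirmed, and the bounded effect on an arm's healing rate worked out above. There would also be occasional extra prompt liver-test or INR repeats for cases that are now only laboratory triggers, because path A allows a week for the repeat and does not require twice-weekly checks.
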